## 4.2. Scientific Rationale for Study Design

### Study Population

A recent study in treatment-refractory patients (including cavitory patients) documented a sputum culture conversion rate of 8.9% by month 6 of guideline-based therapy. This patient population therefore represents not only an area of unmet medical need, but also a suitable group to establish whether BDQ is active against human MAC infections. The present study will enroll patients with treatment-refractory MAC-LD defined as participants who are sputum culture positive for MAC despite at least 6 months of MAC-LD treatment (at least 2 antibiotics for MAC, including a macrolide), that is either ongoing or has stopped within the last 12 months.

Regardless of the predominant radiographical MAC-LD clinical presentation (FC type or NB type), the presence of cavities may be correlated with different treatment outcome compared to the noncavitory NB type. Additionally, cavity size may be negatively correlated with treatment outcome, as demonstrated in participants with drug susceptible TB. To uniformly evaluate clinical efficacy, participants with one or more cavities  $\geq 2$  cm on a chest CT scan taken within the last 6 months will be excluded from this study. Patients with large cavity have a poor prognosis and surgical therapy in addition to chemotherapy can be considered immediately after diagnosis.

### Dose Selection

Refer to Section 4.3, [Justification for Dose](#).

### Blinding, Control, Study Phase/Periods, Treatment Groups

The Japanese guidelines currently recommend a 3-drug regimen, consisting of CAM, RFP or RBT, and EB, as SOC. The South Korean and Taiwanese guidelines recommend a 3-drug regimen consisting of macrolide (CAM or AZM), RFP or RBT, and EB as the SOC. Therefore, 3-drug regimen, consisting of CAM as macrolide is selected as control arm.

This study will be conducted by an open-label design. Because rifamycin, which is included in the control regimen, is known to cause a reddish coloration of the urine, feces, sputum, sweat, serum, and discoloration of soft contact lenses, blinding of the study drug/comparator is practically impossible due to the wide area of coloration effects. The primary endpoint at Week 24 is sputum culture conversion, which will be assessed based on the results of culture at the central microbiology laboratory. These microbiological results will be blinded to the investigator and

participants until the completion of the other assessments at Week 24. Randomization will be used to minimize bias in the assignment of participants to treatment groups, to increase the likelihood that known and unknown participant attributes (eg, demographic and baseline characteristics) are evenly balanced across treatment groups, and to enhance the validity of statistical comparisons across treatment groups.

The planned treatment duration of BDQ (48-week BDQ treatment period) is same as the maximum duration in the sponsor-conducted clinical study in Japanese participants with MDR-TB (Study TMC207TBC2001). Overall, the treatment success rate in treatment-refractory patients with the current treatment has been unsatisfactory and many patients remain culture positive despite prolonged therapy. The local guidelines for MAC-LD treatment in Japan, South Korea, Taiwan and an Official ATS/IDSA statement currently recommend treating until patients have been on SOC for 1 year after culture conversion, but there is no evidence to support this treatment duration.

The standard duration of administration with BDQ for the treatment of MDR-TB with a known bactericidal effect is 24 weeks, whereas the duration of administration with BDQ for MAC-LD, where a bacteriostatic effect is suggested, needs to be longer, and is therefore set at 48 weeks and drug free follow-up period for 3 months is planned to evaluate the recurrences after completion of treatment to evaluate appropriate treatment duration. On the other hand, the participants in Group B who achieved culture conversion at Week 24 will continue up to Week 60. This 60-week duration is consistent with the end of follow-up period in Group A. Upon completion of the 60-week study intervention period, the study is completed, but the participant may continue SOC of local guidelines in Japan, South Korea and Taiwan or medical practice at each study site for least 1 year after culture conversion at the discretion of the investigators after study completion.

In addition, participants who have not achieved culture conversion in Group A (BDQ-containing regimen) will continue their assigned regimen until Week 48, unless they have difficulty continuing due to failure to respond (see Section 6.8.1, based on non-conversion and clinical worsening) or the occurrence of AE related to the regimen. If participants were judged to have difficulty continuing due to failure to respond to the regimen or the occurrence of the regimen related AE, at the discretion of investigators, there will be options to discontinue from the study or switch to an individualized treatment regimen (in principle, add on injectable SM, injectable or inhalation suspension of AMK).

The participants in Group B (rifamycin-containing regimen) who do not achieve culture conversion up to Week 24 and continue the study, will have the option, at discretion of investigator, to (1) continue rifamycin-containing regimen, (2) switch to individualized treatment regimen (see Section 6.8.1, in principle, add on injectable SM, injectable or inhalation suspension of AMK), (3) switch to BDQ-containing regimen after 2-week washout of rifamycin. The latter option is called the "optional cohort" (see Section 6.8.2). The target population is refractory participants, who received at least 6-month SOC before this study and received the rifamycin-containing regimen up to Week 24 and SOC for at least 1 year but could not achieve culture conversion. Therefore, in consideration of the benefits for non-converters in Group B, an opportunity to switch to the optional cohort at Week 24 after the completion of the assessments will be provided. All

participants switched to individualized treatment regimen or the optional cohort will be considered as “treatment failures”.

### **Efficacy Measures**

To date, the surrogate markers predictive of clinical treatment response in MAC-LD have not been established. In 2018, a consensus paper on treatment outcome definitions was released which proposed key outcome parameters to be used in the treatment of NTM-LD. The microbiological consensus definition for culture conversion is the finding of at least 3 consecutive negative mycobacterial cultures from respiratory samples, collected at least 4 weeks apart (at least 25 days apart in consideration of allowed visiting window), during antimycobacterial treatment (the sampling date of the first negative culture is then the date of culture conversion). In the present study, the primary endpoint for the primary analysis at Week 24 is the percentage of participants achieving sputum culture conversion (defined as 3 consecutive negative sputum cultures taken at least 25 days apart) (ie, 6 months after start of study intervention). The recent study using semiquantitative cultures to monitor treatment effect suggests that a lack of microbiological response after 6 months of treatment is a very accurate predictor of treatment failure (nonresponse) at 12 months and beyond. The percentage of participants achieving sputum culture conversion at Week 48 (ie, 12 months after start of study intervention) is the secondary efficacy endpoint for the assessment of the sustainability of sputum culture conversion. In addition, the secondary efficacy endpoint for clinical assessment is the change from baseline in patient-reported health status on the total score of SGRQ and the extrapolatory efficacy endpoint for clinical assessment is the change from baseline in patient-reported health status on the score of QOL-B NTM module at Weeks 24, 48, and 60.

The burden of living with MAC-LD and the complicated, prolonged therapy associated with its treatment has a significant impact on patient’s HRQOL. Assessing HRQOL is an important aspect of patient assessment and management, which involves evaluating a patient’s satisfaction with domains of health, including the perception of performance in physical function, emotional state, social interaction, and somatic sensation domains. The present study will evaluate the HRQOL in participants with MAC-LD using the SGRQ and the QOL-B NTM module. The SGRQ is a disease-specific instrument designed to measure impact on overall health, daily life, and perceived well-being in participants with obstructive airway disease. The NTM module was developed specifically for NTM symptoms and consists of NTM symptoms, body image, digestive symptoms, and eating problems. However, as QOL-B NTM module has only been preliminarily validated and no consensus has been reached at present, this will be handled as an exploratory measurement tool in this study.

#### **4.2.1. Study-specific Ethical Design Considerations**

Potential participants will be fully informed of the risks and requirements of the study and, during the study, participants will be given any new information that may affect their decision to continue participation. They will be told that their consent to participate in the study is voluntary and may be withdrawn at any time with no reason given and without penalty or loss of benefits to which they would otherwise be entitled. Only participants who are fully able to understand the risks, benefits, and potential AEs of the study, and provide their consent voluntarily will be enrolled.

The primary ethical concern is to continue the standard regimen which may not be effective in treatment-refractory MAC-LD for at least Week 24 in case participants will be randomized to Group B. Although this study plans to perform the primary analysis at Week 24, an optional cohort of participants randomized to standard therapy who have not achieved culture conversion at Week 24 will be provided in which they will receive the BDQ combination regimen. Participants who are not converted at Week 24 will be selected at the discretion of the investigator to either continue with the treatment regimen used through Week 24, switch to an individualized treatment regimen, or proceed to an optional cohort and receive the BDQ combination regimen. All participants, except those who continue on the same treatment regimen through Week 24, will be treated as failures. This cohort was set as a rescue measure for participants assigned to the standard therapy because the sputum culture conversion rate by the standard therapy was low and the likelihood of conversion was low even if the treatment was continued for longer than 24 weeks.

Addition of aminoglycosides (injectable SM, injectable or inhalation suspension of AMK) is permitted as an individualized treatment regimen in either treatment group if participants are judged to have difficulty continuing the designated treatment regimen due to failure to respond (based on non-conversion and clinical worsening) or the occurrence of the regimen related AE, at the discretion of investigators. Addition of aminoglycosides in Group B is recommended by the Japanese guideline, and is expected to be clinically efficacious in participants with clinical worsening. On the other hand, addition of aminoglycosides to the regimen in Group A has been confirmed to have antimicrobial activity based on nonclinical studies, but its clinical efficacy has not been confirmed at present. Regarding safety, in the Japanese and oversea guidelines on approved drug therapies for the treatment of pulmonary MDR-TB, AMK and SM are recommended as agents to be used in combination with multiple drug therapies including BDQ, and there have been no reports of any problems concerning drug interactions and new adverse reactions associated with the combination use. However, experience in the treatment of pulmonary MAC disease is limited, and safety monitoring participants will be performed at least every 4 weeks until study completion or early discontinuation according to Section 1.3, [Schedule of Activities \(SoA\)](#). Since treatment options for participants who failed to respond are limited, addition of aminoglycosides, which is expected to convert and improve clinical symptoms, was selected as an individualized treatment regimen.

The total blood volume to be collected is considered to be an acceptable amount of blood to be collected over this time period from the population in this study based upon the standard of the Japanese Red Cross Society.

### 4.3. Justification for Dose

The dosage and administration of BDQ of this study in adult participants with treatment-refractory MAC-LD (BDQ 400 mg once daily in the first 2 weeks, followed by BDQ 200 mg twice weekly in Weeks 3-48) was determined based on the PK results of DDI study between CAM and BDQ and simulation using the previously developed population pharmacokinetic (popPK) model of BDQ.

In this study, the replacement of RFP in the current standard therapy regimen (CAM + EB + RFP) with BDQ (CAM + EB + BDQ) for the participants with treatment-refractory MAC-LD is planned. BDQ is a CYP3A4 substrate and co-administration with CAM (CYP3A4 inhibitor), one of the standard therapies for MAC-LD, increases BDQ exposure. Thus, a popPK model was developed to simulate the exposure of BDQ in combination with CAM. As the popPK model of BDQ, a model based on the non-Japanese data from Phase 1 and Phase 2 studies conducted at the timing of development for the participants with MDR-TB was used. Applying this model to the results from NTM1001, a 37% decrease in BDQ clearance was estimated when CAM was co-administered. The model was used to explore the dosage and administration of BDQ in this study. Bedaquiline exposures were targeted to be similar to those expected with the MDR-TB dosing regimen (BDQ 400 mg once daily in the first 2 weeks, followed by BDQ 200 mg three times weekly in Weeks 3-24) for the following reasons:

- There were no safety concerns in the Phase 2 clinical studies in non-Japanese and Japanese participants with MDR-TB.
- Based on the postmarketing safety information of BDQ in Japan, there has been no safety concern in participants with MDR-TB, even when administered for longer than 24 weeks.

In this assessment, several dose regimens were simulated. When BDQ PK was simulated for 1,000 participants under the dose regimen of “BDQ 400 mg once daily in the first 2 weeks, followed by BDQ 200 mg twice weekly in Weeks 3 to 48 (in combination with CAM 500 mg twice daily)”, the exposure was consistent with that expected with the dosage regimen for pulmonary MDR-TB (Table 1).

**Table 1: The Ratios of Mean BDQ Exposures From Simulations of the Dose and Administration of BDQ for the Patients With MDR-TB (MDR-TB regimen) and the Dose and Administration of BDQ for the Patients With MAC-LD in This Study (MAC-LD regimen)**

Time since first BDQ dose	The ratio a of C trough b	The ratio a of C max	The ratio a of AUC
Week 2	1.15	1.06	1.11 c
Week 24	0.97	0.98	0.93 d
Week 48	0.99	0.99	0.95 d

Key: AUC=area under curve; CAM=clarithromycin; Cmax=maximum plasma concentration; Ctrough=minimum plasma concentration between 0 hour and the dosing interval  $\tau$ ; MAC-LD=*Mycobacterium avium* complex-lung disease; MDR-TB=multi-drug resistant tuberculosis.

Note: In MDR-TB regimen, BDQ was administered as 400 mg once daily in the first 2 weeks, followed by BDQ 200 mg three times weekly in Weeks 3 to 24 (without co-administration of CAM).

MAC-LD regimen: BDQ 400 mg once daily in the first 2 weeks, followed by BDQ 200 mg twice weekly in Week 3 to 48 (with co-administration of CAM [500 mg twice daily]).

a: The mean exposure of MAC-LD regimen/ the mean exposure of MDR-TB regimen

b: Plasma trough concentration

c: AUC24h

d: AUC168h.

As a result, BDQ dosing regimen for this study was proposed as “400 mg once daily for the first 2 weeks in combination with CAM followed by BDQ administered at 200 mg twice weekly for the next 46 weeks, with an interval of at least 72 hours”.

## 4.4. End of Study Definition

### End of Study Definition

The end of study is considered as the last visit for the last participant in the study. The final data from the study site will be sent to the sponsor (or designee) after completion of the final participant visit at that study site, in the time frame specified in the Clinical Trial Agreement.

### Study Completion Definition

A participant will be considered to have completed the study if he or she has completed assessments at Week 60 of the open-label phase or at OPW48 of the optional cohort. Following completion of the study, the participant may continue the SOC per local guidelines or medical practice at each study site for at least 1 year after culture conversion, at the discretion of the investigator.

## 5. STUDY POPULATION

Screening for eligible participants will be performed within 10 weeks before administration of the study intervention.

The inclusion and exclusion criteria for enrolling participants in this study are described below. If there is a question about these criteria, the investigator must consult with the appropriate sponsor representative and resolve any issues before enrolling a participant in the study. Waivers are not allowed.

For a discussion of the statistical considerations of participant selection, refer to [Section 9.2, Sample Size Determination](#).

### 5.1. Inclusion Criteria

Each potential participant must satisfy all of the following criteria to be enrolled in the study:

1. Male or female.
2. 20 to 79 years of age, inclusive.
3. Has body weight  $\geq 40$  kg at screening and on Day 1.
4. Has radiological evidence consistent with NTM-LD based on a chest CT scan taken within 6 months prior to screening or at screening.
5. Criterion modified per Amendment 4.
- 5.1 Criterion modified per Amendment 8.
- 5.2 Has at least 2 positive sputum cultures of MAC (sputum cultures to be taken at least 4 weeks apart):

- one obtained within 12 months prior to screening, which was documented while being treated for MAC-LD for a total of at least 6 months.
  - one at screening (by central microbiology laboratory).
6. Criterion modified per Amendment 4.
- 6.1 Criterion modified per Amendment 8.
- 6.2 Received at least 6 months of consecutive MAC-LD treatment (at least 2 antibiotics for MAC, including a macrolide), that is either ongoing or has stopped within 12 months prior to screening.
- Note: Participants must be compliant with medication intake for at least 75% of the total doses for prescribed SOC (including intermittent regimen) recommended by local guidelines. Participants who have missed more than 25% of their doses during a given treatment period for any reason (including noncompliance by participants, interruption due to an AE at the discretion of physician, and others) can only be enrolled if approved by the sponsor's medical monitor.
7. No presence of cognitive dysfunction that would impact the completion of the patient-reported outcome (PRO) assessments.
8. Must sign an informed consent form (ICF) indicating that he or she understands the purpose of, and procedures required for, the study and is willing to participate in the study.
9. A woman of childbearing potential must have a negative highly sensitive serum ( $\beta$ -human chorionic gonadotropin [ $\beta$ -hCG]) test at screening and on Day 1.
10. A woman using oral contraceptives must use an additional contraceptive method (as required in Inclusion Criterion 11).
11. A woman must be (as defined in Section 10.5, [Appendix 5: Contraceptive Guidance](#)).
- a. Not of childbearing potential
  - b. Of childbearing potential and
    - Practicing a highly effective method of contraception (failure rate of <1% per year when used consistently and correctly) and agrees to remain on a highly effective method while receiving study intervention and until 90 days after last dose - the end of relevant systemic exposure. The investigator should evaluate the potential for contraceptive method failure (eg, noncompliance, recently initiated) in relationship to the first dose of the study intervention. Examples of highly effective methods of contraception are located in Section 10.5, [Appendix 5: Contraceptive Guidance](#).

12. a woman must agree not to donate eggs (ova, oocytes) or freeze for future use for the purposes of assisted reproduction during the study and for at least 90 days after receiving the last dose of study intervention.
13. a male participant must wear a condom when engaging in any activity that allows for passage of ejaculate to another person during the study and for at least 90 days after receiving the last dose of study intervention (male participants should also be advised of the benefit for a female partner to use a highly effective method of contraception as condom may break or leak).
14. a male participant must agree not to donate sperm for the purpose of reproduction during the study and for a minimum 90 days after receiving the last dose of study intervention.

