- w. Examination of height (screening only), body weight measurement, observation for skin events/reactions, assessments performed as part of the clinical course of NTM related disease (body temperature, heart rate, respiratory rate, and oxygen saturation) and additional assessments (systolic blood pressure and diastolic blood pressure). Physical examination and vital signs will be performed before intake of study intervention and blood sampling.
- x. Including hematology, chemistry and urinalysis.
- y. Including visual acuity, color discrimination, visual field. Audiology and visual examinations within 4 week prior to Day 1 and within 4 days prior or after each visit other than Day 1 will be acceptable.
- z. After Week 24 assessment, all participants in the Group B who are non-conversion and well-tolerated, will be considered to receive the BDQ-containing regimen at the discretion of the investigators. When the investigator changes to BDQ-containing regimen, 2-week washout of treated rifamycin must be given before initiation of BDQ-containing regimen. The investigators can postpone the decision to transfer

to the optional cohort for up to Week 32 in order to confirm a sputum culture positive at Week 24, if necessary. If decision to transfer to the optional cohort exceeds Week 32 for reasons such as time required to obtain the result of microbiology assessment of Week 24, the period may be extended. If necessary, consider study date of OPD1 by adding the number of days required to switch to the optional cohort to study date of Week 24.

- aa. OPD1 is Day 1 for participants who are transferred to optional cohort. Assessments planned on OPD1 must be performed prior to first dose of BDQ. The investigators can postpone the decision to switch to the optional cohort for up to Week 32 in order to confirm sputum culture positive at Week 24. If decision to transfer to the optional cohort exceeds Week 32 for reasons such as time required to obtain the result of microbiology assessment of Week 24, the period may be extended.
- bb. Upon completion of the 48-week optional treatment period, the observation of each participant will be completed.

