## Clinical Studies

### *Phase 1 Studies*

Pooled analyses were done for 8 Phase 1 studies in healthy subjects (5 single-dose studies and 3 multiple-dose studies). The pooled analysis included data from 217 healthy subjects, of whom, 189 received at least 1 dose of BDQ up to 700 mg. Five studies were not included in the Phase 1 pooled analysis: C117 was an open-label, DDI study in 16 HIV-1 infected subjects (without TB infection). This single-sequence DDI Phase 1 study was conducted to investigate the potential interaction between steady-state nevirapine and a single-dose of 400 mg BDQ. C112 was an open-label, single-dose study in 8 healthy subjects and in 8 subjects with moderate hepatic impairment. TBC1003 was a double-blind, single-dose study in 88 healthy subjects to evaluate the effect of a single supratherapeutic (800 mg) dose BDQ on the QT/corrected QT (QTc) interval. A total of 44 subjects received BDQ. TBC1002 was an open-label 3-way crossover study in 36 healthy adults to assess the relative bioavailability of 2 pediatric formulations of BDQ after single-dose administration of 100 mg, with and without food. NTM1001 was an open-label, DDI study in 16 healthy subjects. This single-sequence DDI Phase 1 study was conducted to investigate the potential interaction between steady-state CAM and a single-dose of 100 mg BDQ.

Bedaquiline was well absorbed with  $t_{\max}$  at approximately 5 hours postdose. The  $C_{\max}$  and AUC increased proportionally up to the highest doses studied (700 mg single dose and 400 mg once daily [qd] multiple doses). Accumulation from Day 1 to Day 14 was approximately 2-fold expressed as increase in AUC, corresponding to an effective half-life of about 24 hours. From Phase 2 study, 4 weeks after ceasing BDQ intake, the mean BDQ and M2 concentrations were reduced by approximately 40% compared to the end of the BDQ treatment period. At the last follow-up visit (Week 120), BDQ and M2 plasma concentrations were approximately 15% and 20% of the median Week 24 plasma concentrations, respectively. The average  $t_{1/2 \text{ term}}$  of BDQ and M2, was estimated as 5.5 months and 5.3 months, respectively.

Administration of BDQ as the tablet formulation with food increased the relative bioavailability (by 95%) compared to administration without food.

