  17. Received an investigational study intervention or used an invasive investigational medical device within 60 days before the planned first dose of study intervention or is currently enrolled in an investigational study.
  18. Is pregnant, or breast-feeding, while enrolled in this study or within 90 days after the last dose of study intervention.
  19. Plans to father a child while enrolled in this study or within 90 days after the last dose of study intervention or who is unwilling to use acceptable methods of contraception as outlined in Section 10.5, [Appendix 5: Contraceptive Guidance](#).
  20. Has any condition for which, in the opinion of the investigator, participation would not be in the best interest of the participant (eg, compromise the well-being) or that could prevent, limit, or confound the protocol-specified assessments.
  21. Has preplanned surgery or procedures that would interfere with the conduct of the study.  
  
Note: Participants with planned surgical procedures to be conducted under local anesthesia may participate.
  22. Employee of the investigator or study site, with direct involvement in the proposed study or other studies under the direction of that investigator or study site, as well as family members of the employees or the investigator.

23. Is co-infected with NTM species other than MAC on sputum culture at screening.

Note: If both MAC and NTM species other than MAC were detected on screening sputum culture, and previous test result(s) suggested possible contamination such as NTM species other than MAC was not detected before screening, a retesting of screening sputum culture (repeat of sputum collection and sputum culture) will be allowed once. The time required for retesting will not be included in the duration of the screening period (9 weeks).

**NOTE:** Investigators should ensure that all study enrollment criteria have been met at screening and at baseline (Day 1). If a participant's clinical status changes (including any available laboratory results or receipt of additional medical records) after screening but before the first dose of study intervention is given such that he or she no longer meets all eligibility criteria, then the participant should be excluded from participation in the study.

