#### 5.3.1. Activity

1. Participants will abstain from strenuous exercise for 24 hours before each blood collection for clinical laboratory tests. Participants may participate in light recreational activities during studies (eg, watching television, reading).
2. Strenuous exercise may affect study specified assessments and safety laboratory results; for this reason, strenuous exercise should be avoided within 24 hours before all planned study visits and during stays in the study site.
3. Avoid donating blood for at least 30 days after last dose of BDQ of the study.

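### Inclusion criterion 11 says relevant exposure has ended 90 days after the last dose, but the protocol's own pharmacokinetic figures leave about half of the bedaquiline level at that time

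*Protocol*

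**What the plan says.** **The windows (Protocol, Sections 5.1 and 5.2).** For women of childbearing potential, criterion 11 requires highly effective contraception during study intervention and "until 90 days after last dose - the end of relevant systemic exposure". This is the only window with an exposure reason.

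- Criteria 12 (egg donation) and 13 (condom use) apply "for at least 90 days after receiving the last dose of study intervention".
- Criterion 14 (sperm donation) applies "for a minimum 90 days after receiving the last dose of study intervention".
- Exclusion 18 reads "Is pregnant, or breast-feeding, while enrolled in this study or within 90 days after the last dose of study intervention", and exclusion 19 uses the same 90 days for planning to father a child.

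**The exposure figures (Protocol, Section 2.2, Phase 1 Studies).** Mean bedaquiline and M2 concentrations were about 40% lower four weeks after stopping. For Week 120, when follow-up ended, the protocol reports that "BDQ and M2 plasma concentrations were approximately 15% and 20% of the median Week 24 plasma concentrations, respectively". Terminal half-life, averaged for each of the two compounds, "was estimated as 5.5 months and 5.3 months, respectively".

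**Pregnancy follow-up.** The Schedule of Activities (Section 1.3) places the last pregnancy test at Week 60 or at early discontinuation. In the optional cohort (Section 1.3.1) the last test is at OPW48 or at early discontinuation. Footnote bb adds: "Upon completion of the 48-week optional treatment period, the observation of each participant will be completed". Section 4.1 says that Group A non-converters at Week 48 leave the study and change regimen if they continue chemotherapy.

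**The concern.** Criterion 11 gives a factual reason for its window. Section 2.2 appears to say something different about bedaquiline and its metabolite: 90 days is little more than half of one terminal half-life. A participant who must accept the window in order to enrol is given a reason that the protocol's own data do not bear out.

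The matter is one of participant safety and of the accuracy of what participants are told. It touches no endpoint, estimand or sample size. It concerns only those who receive bedaquiline, that is, Group A and the Group B participants who move to the optional cohort.

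A second question follows. If a window is stated, does the plan look for pregnancies within it? For two groups of bedaquiline recipients, scheduled contact ends at about the last dose.

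**Working it through.** **Inputs (Protocol, Section 2.2).** Terminal half-life is 5.5 months for bedaquiline and 5.3 for M2. The residual at 4 weeks is about 60% for both. The residual at Week 120 is 15% for bedaquiline and 20% for M2. A month is taken as 30.44 days.

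**Assumptions.** Dosing behind the Week 24 and Week 120 figures stopped at Week 24, the standard course length given in Section 2.1. Week 120 is then 96 weeks, or 672 days, off drug. The washout of earlier studies is applied to 48 weeks of dosing here.

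**Step 1: the window in half-lives.** For bedaquiline 5.5 × 30.44 = 167.4 days, and 90/167.4 = 0.54. For M2 5.3 × 30.44 = 161.3 days, and 90/161.3 = 0.56.

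**Step 2: fraction of the end-of-treatment level left at day 90.**

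| Method | Bedaquiline | M2 |
|---|---|---|
| Half-life alone, 2^(−90/t½) | 69% | 68% |
| 60% at day 28, then the stated half-life for 62 days, 0.60 × 2^(−62/t½) | 46% | 46% |
| Log-linear from 60% at day 28 to the Week 120 residual | 53% | 54% |

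In the last row, the bedaquiline fall from 60% to 15% is two halvings in 672 − 28 = 644 days, an apparent half-life of 322 days. So 0.60 × 2^(−62/322) = 0.525. For M2 the apparent half-life is 644/log2(0.60/0.20) = 406 days, and 0.60 × 2^(−62/406) = 0.54.

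**Step 3: sensitivity.**

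- Reading the 4-week bedaquiline residual as 55% to 65% moves the central range to 43% to 56%.
- Extending the fast first-month slope to day 90 gives 0.60^(90/28) = 19%. This is a floor for any multi-exponential decline through the 4-week point, because such a curve only flattens.
- Section 2.2 also gives an effective half-life of about 24 hours, derived from accumulation. Used for washout, it would leave 2^(−28), practically nothing, at 4 weeks. The stated 60% rules that out.

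**Step 4: consistency of the inputs.** The figures do not lie on one curve. Sixty per cent at day 28 followed by a 5.5-month half-life predicts 0.60 × 2^(−644/167.4) = 4% at Week 120, against the stated 15%. The mismatch points to slower elimination, so it does not weaken the result.

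**Step 5: scheduled follow-up against the window.** In the optional cohort the last dose and the last visit are both nominally at OPW48, so no scheduled test or enquiry falls in the 90 days after it. Group A non-converters who leave at Week 48 are in the same position. On the planning figures (10% plus 20 points, so 30% conversion in Group A at Week 24), this second group could be most of Group A if Week 48 conversion were similar. That is an assumption, not a forecast in the documents.

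**The case against.** **The word *relevant*.** This is the strongest defence. Criterion 11 does not say that exposure has ended, only that relevant exposure has. Section 2.2 shows that drug remains. It does not show that the remaining level matters for reproduction. Fuller nonclinical information is referred to the Investigator's Brochure. The protocol also uses limits shorter than full elimination elsewhere: Section 6.8 lets some interacting and myopathy-risk drugs restart one month after bedaquiline stops. So a reader might infer that the window is too short or that participants are at reproductive risk, and the documents support neither. What they do show is that no passage defines *relevant*, gives a threshold, or links 90 days to one. Section 8.2.3, by contrast, cites the long half-life as a reason to continue ECG monitoring after the last dose.

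**The other windows.** A reader might infer that every contraception and donation window contradicts the half-life. That does not follow. Criteria 12 to 14 set minimum periods, and exclusions 18 and 19 give no exposure reason. The blood-donation rule in Section 5.3.1, "Avoid donating blood for at least 30 days after last dose of BDQ of the study", makes no exposure claim either. The spermatogenesis cycle of about 74 days in Section 10.5 is not linked to any window and would not support an exposure label.

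**Follow-up.** A reader might infer that pregnancies in the window go wholly unobserved. Section 8.3.5 requires a known pregnancy, including in a partner, to be reported within 24 hours of the site learning of it, with follow-up of the outcome. It treats abnormal outcomes as serious adverse events, and Section 8.3.1 covers serious events reported to the investigator within 30 days of the last dose. These are real safeguards, but they rely on someone volunteering the information. The extra tests allowed by Section 8.2.5 apply only during participation. For Group A converters, Weeks 48 to 60 span 84 days nominally and 76 to 92 days with the ±4-day windows. That nominal 6-day shortfall is not a basis for criticism.

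**One window for both arms.** A common minimum is a defensible simplification, since Group B non-converters may move to bedaquiline. Nothing here shows that separate windows are needed.

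**Conclusion.** The point holds for criterion 11. For bedaquiline recipients, its exposure label is inconsistent with Section 2.2, which implies about 46% to 53% of the end-of-treatment level at day 90 (M2 46% to 54%). The half-life alone gives 69% (M2 68%). The result rests on washout data from earlier studies, an assumed 24-week course behind the Week 120 figure, and their transfer to 48 weeks of dosing with clarithromycin. No reasonable reading of the stated figures brings the residual close to zero.

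For criteria 12 to 14 and exclusions 18 and 19, the 90 days is unexplained rather than contradicted. In the optional cohort after OPW48, and for Group A non-converters who leave at Week 48, the window relies on spontaneous reporting alone.

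This is worth correcting because it is a safety rule that participants must accept. The number of women of childbearing potential is probably small, though the documents give no figure. Criteria 13 and 14 apply to every male participant.

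**What to change.** - Reconcile criterion 11, and the criteria that share its window, with the exposure figures in Section 2.2. Either state the basis on which exposure at the chosen time is no longer relevant, or revise the statement.
- Carry the result into the consent form.
- Reconcile the end of scheduled pregnancy follow-up with whatever window is stated, for the optional cohort after OPW48 and for Group A non-converters who leave at Week 48.

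No window or follow-up time is proposed here; that is for the sponsor's clinical and safety experts.

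The cost is wording in Sections 5.1 and 5.2 and in the consent form. The follow-up item may need only a remote contact, but that depends on the window. If contact had to extend well beyond Week 60 or OPW48, the completion definition in Section 4.4 would need attention too. Sample size and analysis are unaffected.
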